### 9.4.2. Hungary: National Health Insurance Fund Administration (NHIFA)

Hungary has a single-payer healthcare system with a purchaser-provider split model and output-based payment system. The budget of the Health Insurance Fund (HIF), managed by the National Health Insurance Fund Administration (NHIFA), consists of health insurance contributions, health care taxes, government transfers, and other incomes. Participation in health insurance is mandatory. Coverage is theoretically universal, as patients cannot be penalized for missed contributions. Family doctors are intended to be gatekeepers, however, certain specialties are accessible without referral (dermatology; ear, nose and throat diseases; obstetrics and gynaecology; general surgery; traumatology; ophthalmology; oncology;

urology; and psychiatry). The NHIFA database contains information on healthcare covered by the state and has national coverage for reimbursed services (medicine, out- and inpatient services), but non-reimbursed services (including over the counter medications) are not included. Data are available for retrospective analyses from 01 January 2004.

There are four NHIFA registers: Demography, Drugs, Inpatient, and Outpatient. The Demography register includes sex, age, and date of death. The Drugs register captures brand information, date, ATC7 codes, volume, ICD codes, and territory. Further, information is collected regarding EU number, invented name, strength, pharmaceutical form, route of administration, packaging, and content. The Inpatient register comprises date (admission, discharge, and length of stay), location, ICD codes, Diagnosis Related Groups (DRG), and International Classification of Procedures in Medicine (ICPM) codes. The Outpatient register captures labs and diagnostic services and specialist visits, including date, location, ICD codes, and ICPM codes.

### 9.4.3. The Netherlands: The PHARMO Database Network

The PHARMO Database Network is a population-based network of electronic healthcare databases and combines anonymous data from different primary and secondary healthcare settings in the Netherlands. All electronic patient records in the PHARMO Database Network include information on age, sex, socioeconomic status, and mortality. The databases are linked on an annual basis, meaning that the average lag time of the data is approximately 1 year (the updated databases are available in the second half of the year). The PHARMO Database Network is broadly representative of the Dutch population and covers both primary and secondary (inpatient and outpatient) settings of care, as well as pharmacy (community and in-patient) dispensed treatments through its different databases.

The different databases in the network include:

- The General Practitioner Database captures electronic medical record (EMR) data from registered GPs (covering approximately 20% of the Dutch population). Key variables include diagnoses (coded via the International Classification of Primary Care [ICPC]), symptoms, laboratory tests and test results, referrals to specialists, and drug prescription information including type of product (ATC codes), prescription date, strength, dosage, regimen, quantity, and route of administration. Height, weight, tobacco use, and alcohol abuse information are also available.
- The Out-patient Pharmacy Database (covering approximately 25% of the Dutch population) includes data on all GP or specialist prescribed products, as well as hospital pharmacies. -The Outpatient Pharmacy Database captures drug dispensings from outpatient pharmacies. Key variables include product (ATC codes), dispensing date, strength, dosage regimen, quantity, route of administration, prescriber specialty, and costs.
- The In-patient Pharmacy Database captures inpatient medication administrations and drug dispensings from hospital pharmacies (covering approximately 10% of the Dutch

population). Key variables include drug type (ATC codes), start and end date of use, strength, dosage regimen, and route of administration.

- The Clinical Laboratory Database captures the results of laboratory tests requested by GPs and medical specialists (covering approximately 5% of the Dutch population). Key variables include date and time of testing, test result, unit of measurement, and type of clinical specimen.
- The Hospital Database, including the high-budget impact medication database (where tofacitinib will be captured), captures hospital admission data for admissions of more than 24 hours or admissions of less than 24 hours that require a bed(covering approximately 80% of the Dutch population). Key variables include information on discharge diagnoses (coded according to the WHO International Classification of Disease and ICD-10), procedures (coded via the Dutch Hospital Data Foundation registration system), and hospital admission and discharge dates.
- The Cancer Registry Database captures cases of newly diagnosed cancer (with national coverage). Key variables include cancer diagnosis, tumour staging (according to tumour, nodes, metastases [TNM] staging), tumor site (topography), morphology (histology; coded via the ICD-O-3), comorbidity at diagnosis, and treatment received directly after diagnosis.
- The Netherlands Perinatal Registry is maintained by Perined and comprises data on pregnancies, births, and neonatal outcomes of births in the Netherlands, voluntarily collected by perinatal caregivers, mainly for benchmarking. For research purposes the data are linked with the PHARMO Database Network via a trusted third party, resulting in the PHARMO Perinatal Research Network (PPRN20). Records include information on mothers (e.g., maternal age, obstetric history, parity), pregnancy (e.g., mode of conception, mode of delivery), and children (e.g., birth weight, gestational age, Apgar score). Diagnoses and symptoms are coded according to the Perinatal Registry code lists.

These data sources are linked on a patient level through probabilistic linkage based on validated algorithms. The number of analysable patients for a given outcome will be limited by the availability of patient data in the databases required to be linked for that outcome. The longitudinal and ongoing nature of the PHARMO Database Network system enables follow-up of more than 10 million residents of the Netherlands for an average of 12 years.

### 9.4.4. Germany: Gesetzliche Krankenversicherung (GKV) claims (SHI Database)

Germany has a multi-payer healthcare system consisting of a combination of statutory health insurance (SHI)—i.e., the Gesetzliche Krankenversicherung (GKV)—and private health insurance (PHI). GKV claims collects German healthcare data based on insurance claims from approximately 8-10 different SHI providers. Since an SHI is a requirement for individuals with a permanent place of residence in Germany, even for short-term stays, the general population coverage in the SHI is considered nationwide. The SHIs also allow insurance coverage for children and spouses within a family insurance policy. The population size available through this claims database is approximately 5 million individuals which represents an estimated 6.9% of the SHI-insured population in Germany and is nationally representative. Available data history reaches back to January 2011. In the database all individuals have a de-identified ID; therefore, longitudinal follow-up is possible. The database includes information on patient demographics and inpatient and outpatient care, as well as outpatient medical prescriptions. Available demographic information includes sex, age, insurance status, time insured, and region of residence. Inpatient and outpatient diagnoses are coded via International Classification of Disease, 10th Revision, German Modification (ICD-10-GM) codes and procedures are available. For outpatient diagnoses, only the quarter of the diagnosis is reported (i.e., the actual date is unavailable). Outpatient physician specialty information and inpatient medical department of care can be accessed. Medical prescriptions from retail pharmacies are coded using the ATC hierarchy and the date of the prescription dispensing is available. Information on patient anthropometric data (e.g., height, weight, body mass index [BMI]) is not available nor are result outcomes for laboratory tests (e.g., ALC, blood lipid levels) or clinical measurements (e.g., blood pressure).

Data for the previous year are updated in the 3rd quarter of the following year, implying a 9--12-month lag for data availability. Furthermore, IQVIA cannot access the data directly and must secure access through a partner, which can take an additional 4-5 months.

### 9.4.5. Summary of databases

A summary of the selected databases is provided below in Table 4.

Characteristics	Sweden NPR, PDR, MBR, NCR, and CDR	Hungary NHIFA	The Netherlands PHARMO Database Network	Germany GKV claims
Database type	Administrative records	Claims	EMRs	Claims
Country population	10.4 million (as of 2020)	9.8 million (as of 2020)	17.4 million (as of 2020)	83.2 million (as of 2020)
Overall representativeness	National coverage	National coverage	National coverage	National coverage
Physician population	NPR: All except GPs PDR: Almost complete coverage	All	All	All
Expected number of tofacitinib patients by the end of 2021	~3400ª	450 b, c	280 d	1111 e
Lag in data availability	14-21 months	6 months	Approximately 12 months	At least 12 months

Table 4.Summary of selected databases

Table 4.	Summary	of selected	databases
----------	---------	-------------	-----------

Characteristics	Sweden	Hungary	The Netherlands	Germany
	NPR, PDR, MBR, NCR, and CDR	NHIFA	PHARMO Database Network	GKV claims

Abbreviations: CDR = [Swedish] Cause of Death Register; EMR = electronic medical record; GKV = Gesetzliche Krankenversicherung; GP(s) = general practitioner(s); MAH = Marketing Authorisation Holder; NHIFA = National Health Insurance Fund Administration; MBR = [Swedish] Medical Birth Register; NCR = [Swedish] National Cancer Registry; NPR = [Swedish] National Patient Register; PDR = [Swedish] Prescribed Drug Register.

- a. Based on tofacitinib data for 2017-2019 that was obtained using the publicly available tools for querying the Swedish national health registers (available at https://sdb.socialstyrelsen.se/if\_lak/val.aspx).
- b. Patient counts provided by the MAH.
- c. Patient counts are through 2022 given the shorter data lag (6 months) associated with NHIFA.
- d. Patient counts as of 2019. This number will decrease when the GP database and the Clinical Laboratory Database are required, because only 30% and 40% of patients observed in the High Budget Impact Medication Dataset are also observed in the GP database (covering approximately 20% of the Dutch population) and the Clinical Laboratory Database (covering approximately 5% of the Dutch population), respectively.
- e. Patient counts 2017-2019.

#### 9.5. Study size

The sample size was based on achieving a desired precision of the estimation for the binary endpoints. The following formula, based on the normal approximation to the binomial proportion, was used to calculate the minimum sample size for significance level  $\alpha$  for each indication per country:

$$n = \frac{P \cdot (1-P) \cdot \left(Z_{1-\alpha/2}\right)^2}{e^2},$$

where *P* is the expected proportion of patients with the outcome of interest; *e* is the margin of error, or half the desired width of the confidence interval (CI); and  $Z_{1-\alpha/2}$  is the standard normal *Z*-score corresponding to a cumulative probability of  $1-\alpha/2$ .

The outcomes of interest are described in Section 9.3.1 (Outcomes) and Table 3. As the proportion of patients with each of the outcomes of interest (p) is not known in advance, it will be set to 50%, which yields the most conservative (i.e., the largest) sample size for a specified margin of error.

Therefore, to obtain 95% CIs with a desired total width of 20% for each outcome of interest (per indication per country), the study will require a sample size of *at least* 97 patients, which is rounded up to a *minimum* target sample size of at least 100 patients per indication per country. Note that the sample size will be smaller for some of the outcomes measured (e.g.,

use of tofacitinib while pregnant [women only] and all outcomes that require patients to have six months of tofacitinib therapy) and thus precision will vary by outcome.

$$n = \frac{0.50 \cdot 0.50 \cdot 1.96^2}{0.10^2} = 96.04$$

As such, the *minimum* target sample size per country (across all three indications) will be 300 patients and the *minimum* target sample size overall (across all countries and all three indications) will be 1200 patients.

Note that the target sample size of 100 patients per indication per country represents a *minimum*—i.e., enrolment will not stop at 100 patients but will rather include *all* patients identified during the indexing period who meet the study inclusion/exclusion criteria. Some indication-country combinations (e.g., RA in Sweden) are likely to have enough patients to have a higher precision (e.g., a confidence interval width closer to 10%) than other indication-country combinations (e.g., UC in Hungary), because tofacitinib has been approved for longer for that indication in that country. The MAH will include all eligible patients within each indication-country combination to maximize the precision of the estimates reported.

If the *minimum* target sample size of 100 patients per indication is not attainable for a country at the end of the study observation period, then the CV and Malignancy Reporting Period 3 will be extended for that country as the data are available.

Table 5 presents the number of patients required for a given indication in each country to achieve select confidence interval widths ranging from 10-20%.

Number of patients	Confidence interval width (%)
385	10
267	12
196	14
151	16
119	18
97	20

 Table 5.
 Number of patients required to achieve select confidence interval widths

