  - The proportion of patients aged 65 years, receiving tofacitinib, who have ≥1 prescription dispensing of tofacitinib from the time they turn 65.5 years old through to the end of the follow-up period and no history of alternative treatments *prior to* that tofacitinib prescription dispensing, reported overall and by approved indication and stratified by VTE Reporting Periodk and CV and Malignancy Reporting Periodl
  - The proportion of patients aged 65 years, receiving tofacitinib, who have ≥1 prescription dispensing of tofacitinib from the time they turn 65.5 years old through to the end of the follow-up period and a history of alternative treatments *prior to* that tofacitinib prescription dispensing, reported overall and by approved indication and stratified by VTE Reporting Periodk and CV and Malignancy Reporting Periodl

<sup>1 Hungary will not have a CV and Malignancy Reporting Period 1 or a CV and Malignancy Reporting Period 2 for PsA and UC.

- Use in patients with CV risk factors, as measured by:e
  - The proportion of patients with evidence of ≥1 CV risk factors *prior to* initiation of tofacitinib, reported overall and by approved indication and stratified by CV and Malignancy Reporting Period
  - The proportion of patients with evidence of ≥1 CV risk factors *prior to* initiation of tofacitinib and no prior use of an alternative therapy (i.e., biologic), reported overall and by approved indication and stratified by CV and Malignancy Reporting Period
  - The proportion of patients who discontinue tofacitinib after developing ≥1 CV risk factor while taking tofacitinib, reported overall and by approved indication and stratified by CV and Malignancy Reporting Period
  - The proportion of patients who continue taking tofacitinib after developing ≥1 CV risk factor while taking tofacitinib, reported overall and by approved indication and stratified by CV and Malignancy Reporting Period
- Use in patients with malignancy risk factors, as measured by:e
  - The proportion of patients with evidence of ≥1 malignancy risk factors prior to initiation of tofacitinib, reported overall and by approved indication and stratified by CV and Malignancy Reporting Period

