#### 9.7.1.3.1. Use in patients with VTE risk factors

The proportion of patients with one or more risk factors for VTE, identified prior to tofacitinib initiation, will be described and tabulated overall and for each individual VTE risk factor (e.g., prior VTE, recent MI) for VTE Reporting Period 1, VTE Reporting Period 2, and VTE Reporting Period 3.vv Proportions will be stratified by "RA or PsA" and "UC."

The total number of VTE risk factors identified prior to tofacitinib initiation will also be described continuously for VTE Reporting Period 1, VTE Reporting Period 2, and VTE Reporting Period 3vv and stratified by "RA or PsA" and "UC."

The proportion of patients diagnosed with UC, one or more VTE risk factors identified prior to tofacitinib initiation, and no use of an alternative therapy (i.e., biologic) prior to tofacitinib initiation whose ADD in Week 16 through Week 23, Week 24 through Week 31, Week 32 through Week 39, and Week 40 through Week 47 was >10 mg will be described and tabulated for VTE Reporting Period 1, VTE Reporting Period 2, and VTE Reporting Period 3.vv

The proportion of patients who discontinue tofacitinib after developing one or more VTE risk factors while taking tofacitinib will be described and tabulated overall and for each individual VTE risk factor (e.g., VTE, MI) for VTE Reporting Period 1, VTE Reporting

ss Patients with  $\geq 2$  dispensings of tofacitinib are more likely to have taken tofacitinib for the full days' supply of the prescription as opposed to patients with only 1 dispensing of tofacitinib.

<sup>tt The study outcomes that contain an ADD component will *not* be assessed in Hungary or the Netherlands. The Hungarian administrative claims database is unable to estimate ADD, either directly or by proxy, due to how tofacitinib is captured in the database. In the high-budget impact medication dataset of the PHARMO Database Network (Netherlands), neither ADD nor the number of pills per prescription is captured.

<sup>uu In GKV claims, outpatient diagnoses are reported quarterly.

<sup>vv Hungary will not have a VTE Reporting Period 1. Hungary will also not have a VTE Reporting Period 2 for PsA and UC.

<sup>ww Hungary will not have a CV and Malignancy Reporting Period 1 or a CV and Malignancy Reporting Period 2 for PsA and UC.

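### Section 9.5 states a 20% confidence-interval width for all outcomes, but near the 100-patient floor it cannot hold for those tabulated by reporting period

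*Protocol*

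**What the plan says.** Section 9.5 uses the normal-approximation precision formula for a single binomial proportion. The expected proportion is unknown, so "it will be set to 50%, which yields the most conservative" sample size. The aim is "to obtain 95% CIs with a desired total width of 20% for each outcome of interest (per indication per country", and the result is a "target sample size of at least 100 patients per indication per country".

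The same section fixes the scope of that aim: "The outcomes of interest are described in Section 9.3.1 (Outcomes) and Table 3". Section 9.3.1 lists the secondary outcomes among them. The CV outcomes, for example, are "reported overall and by approved indication and stratified by CV and Malignancy Reporting Period". Section 9.7.1.3.1 tabulates the VTE outcomes "for VTE Reporting Period 1, VTE Reporting Period 2, and VTE Reporting Period 3". Sections 9.7.1.3.2 to 9.7.1.3.4 do the same for the elderly, CV and malignancy outcomes. Section 9.7.1 plans 95% intervals, when relevant, for the outcomes in 9.3.1 and Table 3.

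Section 9.5 warns that some outcomes will have fewer patients, so that precision will differ between outcomes. Its examples are use in pregnancy and outcomes that need six months of therapy. If 100 patients are not reached, "then the CV and Malignancy Reporting Period 3 will be extended for that country as the data are available". Section 9.2.1 ends VTE Reporting Period 3 on 31 December 2023.

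**The concern.** The formula describes one undivided sample per indication and country. The secondary objective 2 outcomes divide that sample by index date into three periods, so a cell that just meets its minimum has well under 97 patients in most of them. Section 9.5 nevertheless attaches the 20% width to the full outcome list.

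Secondary objective 2 describes use before and after the 2019 and 2021 measures, and Section 9.9 uses before-and-after proportions as its proxy for cautious prescribing in patients with VTE risk factors. A reader who sees that a cell met its target would credit its period estimates with a precision that they lack.

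The extension rule adds a smaller gap. It names only CV and Malignancy Reporting Period 3. As written, a patient indexed after 31 December 2023 belongs to no VTE reporting period.

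**Working it through.** **The plan's own figure.** Inputs from Section 9.5: P = 0.50, z = 1.96, e = 0.10.

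n = P(1 − P)z²/e² = 0.25 × 3.8416 / 0.01 = 96.04, so 97, rounded up to 100. All six rows of Table 5 also reproduce (385, 267, 196, 151, 119, 97). With 100 patients the width is 2 × 1.96 × √(0.25/100) = 19.6%.

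**A bound that needs no accrual assumption.** At P = 0.5 the width is 1.96/√n. If 100 patients fall into three periods, the smallest holds at most 33, and 1.96/√33 = 34.1%. An exact equal split (33.3 each) gives 33.9%. So at least one period has a width of about 34% or more, and at least two periods hold fewer than 97 patients.

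**Illustration under even accrual.** The protocol gives no accrual by indication and period, so uniform accrual of exactly 100 patients is an assumption. Period lengths come from Sections 9.2.1 and 9.2.2. Patients per period = 100 × months in period / total months.

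| Layout | Months | Patients | Widths |
|---|---|---|---|
| VTE, full 81 months | 26/16/39 | 32/20/48 | 34.6%/44.1%/28.2% |
| CV and Malignancy, 9-month Period 2 | 51/9/21 | 63/11/26 | 24.7%/58.8%/38.5% |
| CV and Malignancy, 12-month Period 2 | 51/12/18 | 63/15/22 | 24.7%/50.9%/41.6% |
| VTE, start September 2018 | 9/16/39 | 14/25/61 | 52.3%/39.2%/25.1% |
| CV and Malignancy, start September 2018 | 34/9/21 | 53/14/33 | 26.9%/52.3%/34.2% |

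In Table 2, September 2018 is the original-materials date for UC in Sweden and for PsA and UC in the Netherlands. For the Netherlands, CV and Malignancy Periods 2 and 3 are still to be adjusted in the SAP, so the last row fits UC in Sweden.

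**Sensitivity.** On the full 81-month layouts:

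- Wilson intervals give about 24% to 51%, and exact intervals about 26% to 60%, so the choice of interval does not change the picture.
- At P = 10% the widths fall to about 15% to 35%.
- The pooled RA-or-PsA VTE stratum has a floor of 200. Its widths are 24.5%/31.2%/20.0%.

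**What 20% within a period would take.** It needs 97 patients in that period. Under even accrual over 81 months, the cell totals that put 97 in the shortest period are:

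- VTE: 97 × 81/16 = 491.1, so 492.
- CV and Malignancy, 12-month Period 2: 97 × 81/12 = 654.8, so 655.
- CV and Malignancy, 9-month Period 2: 97 × 81/9 = 873.

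**Which cells are near the floor.** Table 9 counts 40 PsA and 65 UC patients in the Netherlands through 2019. These numbers are expected to grow, but fall where linkage is required. Table 10 counts 843 RA patients in Germany for 2017–2019, and Section 9.5 expects RA in Sweden to come closer to a 10% width.

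**The case against.** The target sentence sets its level as indication and country, and no sentence promises 20% within a reporting period. The caveat on smaller samples is an open list with a general conclusion, so a period subset could be read as one more instance. The 100 is a floor, and all eligible patients are included. P = 50% is the worst case: 62 patients at P = 20% already give 2 × 1.96 × √(0.16/62) = 19.9%. Intervals are planned, so wide ones would be visible in the report.

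Much of this stands. It confines the point to cells near the floor and makes it a matter of stated scope. It does not remove it: the section ties the width to a list of outcomes that are themselves defined by period, and the caveat's examples do not point to a split that affects every secondary objective 2 outcome. Pooling RA with PsA helps only the VTE strata. UC stays alone, and the elderly, CV and malignancy outcomes are reported by approved indication.

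A reader might go further and infer any of the following. The documents do not support them.

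- **The sample-size arithmetic is wrong.** It reproduces exactly.
- **The study must reach a set precision for the change from Period 1 to Period 3.** Section 9.7.1 rules out comparative analyses, and no such difference is specified.
- **The extension rule fails because it adds nobody to an early period.** No extension of a retrospective study could.

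On the VTE end date, Section 6 and Section 9.7 speak of extending the whole observation period, so the sponsor may intend VTE Reporting Period 3 to move too. The text does not say so.

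**Conclusion.** The concern holds as a misstatement of scope in Section 9.5. The 97/100 figure and Table 5 are correct for one proportion over the whole indexing period. The 20% width is not delivered for the same outcomes within reporting periods in a cell near the minimum.

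At P = 50%, with exactly 100 patients and all three periods applicable, at least one period has a width of about 34% or more, whatever the accrual. The range of about 25% to 59% rests on the further assumption of even accrual and is an illustration, not a forecast. PsA and UC in the Netherlands are the realistic examples. RA in Sweden and Germany is likely to be much less affected. PsA and UC in Hungary have no Period 1 or 2 (Section 9.9), so the three-way split does not arise there.

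The missing alignment of VTE Reporting Period 3 with the extension is a minor, separate gap.

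**What to change.** In Section 9.5:

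1. Limit the 20% width statement to proportions estimated over the whole indexing period.
2. State that a 20% width within a reporting period needs 97 patients in that period, at P = 50%.
3. Add a few rows beside Table 5 with illustrative per-period widths at the minimum of 100, under a stated accrual assumption, and name the reporting-period split in the existing caveat.

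In Sections 9.2.1, 9.2.2, 9.5 and 9.5.1, say that where the observation period is extended, VTE Reporting Period 3 is extended together with CV and Malignancy Reporting Period 3, so that added patients enter both sets of analyses.

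The cost is wording and a few table rows. The stated precision for secondary objective 2 becomes less favourable. No extra patients, higher minimum, between-period difference or rule on when to draw conclusions is required.
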